Intervention Procedures: After target enrollment (n=240) is reached, YMCSM Peers will begin the intervention by posting materials according to the timeline developed in the ongoing E-PrEP content project. We will hold weekly project meetings (on different days) with Peers assigned to both E-PrEP and BxNow to ensure appropriate implementation, and to discuss logistical, ethical, or other issues that arise. For participants in the BxNow control arm, Peers will post about general health topics unrelated to HIV or sexual health (e.g. fitness, nutrition, smoking). If a control participant posts a question about PrEP, Peers will refer the individual to the CDC PrEP information site or answer the question privately. Content for both arms will be posted over a 6 week period, and outcome data will be collected via online surveys at baseline, 6, and 12 weeks and after 36 weeks (Table 13). Participants will be given \$20, \$30, and \$40 and 20 online gift-cards or through a Clincard as incentives after completion of assessments at T1, T2, and T3, and T4 respectively.

Anticipated components of E-PrEP: Potential components are listed in Table 2. *However, the exact contents, formats, and mode and timing of delivery of E-PrEP will be informed by input from Peers.*¹²³ We have successfully used this approach in *theSEXword* pilot, with ongoing engagement by participants. We will develop all components for both E-PrEP and the control condition (BxNow), and will also create an intervention activity guide for all 6 weeks, but the exact timeline for intervention delivery will be determined based on findings from Aims 1 and 2. We will thus standardize E-PrEP in its mode of delivery, types of digital media and contents, message framing, and sequence of topics posted and discussed, but Peers will tailor the exact language of posts based on their communication style. Components will be interactive wherever possible; for example, to target a factor such as perceived low risk, participants might assess their risk in an interactive poll, see results in real-time, compare themselves to others, and be engaged by Peers in discussions about risk. To address barriers to access, we might develop a brief time-elapsd video showing where and how to register at a clinic to obtain PrEP. All materials, including assessments, will be smartphone friendly, as most participants use mobile devices.

Table 1. Intervention Timeline

Component	Week	-4	0	6	12	36+
Participant Recruitment						

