Compensation: Participants will be given \$20, \$30, and \$40 and \$20 as incentives after completion of assessments at baseline (T1), 6 weeks (T2), and 12 weeks(T3), and post 36 weeks (T4) (respectively). The participants will be given the choice to receive their incentives either via e-codes, Amazon online-gift cards, or by receiving a Clincard.

Data Collection:

We will collect three general types of data: 1) online processes (e.g. referral source, # of platforms joined by each participant); 2) measures of engagement with intervention components (e.g. # of views, time spent online); and 3) measures of outcome and independent variables, collected through online surveys at the ~~four~~three time points (see Table 2). To help assess both degree of exposure to intervention components and possible contamination between the two conditions, the surveys at 6 weeks (T2), ~~and~~ 12 weeks (T3) will display random samples of study and non-study graphics and posts and ask participants if they recall seeing them, with E-PrEP materials embedded in the choices.^{106,119,141}

Table 2. Data Collection					
Measures	Week	0	6	12	36+
PrEP intention, use, knowledge, attitudes		x	x	x	x
Perceived PrEP attributes		x	x	x	
HIV testing, risk behaviors		x	x	x	
Peer affinity and network data		x	x	x	

Table 2. Data Collection					
Measures	Week	0	6	12	36+
PrEP intention, use, knowledge, attitudes		x	x	x	x
Perceived PrEP attributes		x	x	x	
HIV testing, risk behaviors		x	x	x	
Peer affinity and network data		x	x	x	
Sociodemographic Factors		x			
Sexual Orientation		x			
Healthcare access		x	x	x	
Substance use		x	x	x	
Perceived risk, stigma		x	x	x	
Social media engagement		x	x		
Intervention exposure			x	x	

Data Security:

In order to securing information over the Internet and social media, and protecting participant data, an electronic, password protected and encrypted system will be developed to store analyses, and social media activity will remain private to study participants.¹⁶⁴ Research participants will be informed of how communications are recorded and stored during the online informed consent process. Due to the ever-changing and evolving nature of privacy issues on social media sites, we will review privacy settings for all social media study sites at least every four weeks and adjustments will be made to the study sites as necessary.

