1. <https://www.qualtrics.com/support/survey-platform/survey-module/survey-options/survey-protection/#PreventingRespondentsFromTakingYourSurveyMoreThanOnce>

Furthermore, we will download the raw data and store it in a password protected *and* encrypted file on the office computer of [name]. Only the PIs and research study staff will have access to the full data-set.

Analytic Plan: Our *primary outcome* will be *intention to use PrEP*,⁸³ which we consider a predictor of subsequent use,¹⁴² and will be measured using a Likert scale. We will use ‘intention’ as a proxy given the low likelihood of actual PrEP use.^{83,132,143} *Secondary outcomes* will be PrEP use, knowledge,¹⁴³ perceptions about PrEP¹³⁴ and HIV testing- and risk-behaviors.¹⁴⁴ *Covariates*^{80,81,143,145-148} will include access to medical care (including HIV/STI testing), sexual orientation, HIV and PrEP related stigma, substance use, sociodemographic factors,¹⁴⁴ social media engagement and network data,^{149,169} and perceived affinity to the referring Peer.¹⁵⁰ First, we will compare groups for equivalence at baseline, using chi-square or t-tests as appropriate. In addition, we will determine whether subgroups (e.g., grouped by number of social media sites joined, social media platform(s) used, peer referent, race/ethnicity, and sexual orientation) differ with respect to the primary and secondary outcomes. Relevant differences will be used as covariates in subsequent models. At each time point, we will examine change in our primary outcome variable (*intention to use PrEP*) by using a traditional two-sample test of proportions. To compare differences in outcomes between arms over time, we will use

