repeated measures mixed-effects logistic and linear models, with the treatment arm as a fixed-effect, Peers as a random-effect, and time (as a linear term) as an independent variable. We will also look at residual plots to determine if we need to include non-linear terms for time. Next, we will use hierarchical models to examine the role of secondary outcomes as potential mediators of change over time, e.g. are there differences by condition in PrEP knowledge or perceptions that account for differences in intentions. Finally, we will assess the impact of the exposure arm (E-PrEP or BxNow) and selected covariates (significant in the bivariate analysis at $p < 0.1$) on the primary and secondary outcomes using mixed-effects models. We will also assess the impact of online process and engagement variables on outcomes. To overcome possible limitations due to intra-cluster correlations, we will include a modified sensitivity analysis that examines outcomes in relation to participants' network size and perceived affinity to the Peers. To test *feasibility*, we will assess online process measures, including participation rate (# of individuals screening eligible and then ultimately joining the study), engagement activity (e.g. time spent viewing posted videos, # of responses posted to questions, participation in polls, etc.), and retention (# of participants actively 'leaving' or 'un-joining' a social media study site and # of respondents to follow-up assessments).

Power Analysis: The primary purpose of this study is to test feasibility and to obtain an effect size estimate for a future R01 application. We estimate that a sample size of 220, accounting for up to 20% attrition¹⁰⁶ will provide 80% power to detect an effect size of 20% in E-PrEP vs. 5% in BxNow in the proportion of participants indicating '*intention to use PrEP*' at 6 weeks, with a two-sided $\alpha < .05$. We will also have adequate power to detect a smaller effect size at 12 weeks because of our repeated measures design. This conservative effect size estimate is reasonable, given the novelty of the proposed intervention, the absence of other studies assessing uptake of a biomedical tool in YMSM, and the results of other studies assessing potential interest in PrEP.⁸³

Procedures outlined below have been guided by [name] (Consultant), and by [name] (Consultant), who has extensive experience in conducting online survey and intervention studies with vulnerable populations including MSM.

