Effectiveness measures will come from the online assessments/surveys collected at 0, 6, 12 weeks. We will use a HIPAA compliant web survey software (i.e. SurveyGizmo.com) to collect survey data. This information is stored on HIPAA compliant, encrypted cloud servers. The data will be downloaded to the PI’s secure password protected office computer. Surveys will not contain personal identifiers, but will contain a study ID associated with a participant’s social media profile. The “Key” associating the study ID to a participant’s social media profile will be kept in a password protected encrypted file on the PI’s office computer. It will not be possible using the survey data for anyone to figure out the actual or online identity of a participant. We will also collect de-identified IP addresses to aid us in identifying potentially duplicate respondents.

I.3. Vulnerable population. Young men who have sex with men could be vulnerable due to their status as a **stigmatized population in society and further stigmatization could be possible if their status as a participant in an HIV prevention intervention is revealed.** In the following sections, we discuss these risks and procedures to minimize them and believe that the risks to participation in the proposed study are minimal.

I.4. Potential risks to subjects. We believe that the risks posed to participation in our study are minimal and no greater than what individuals encounter in their regular use of the Internet and social media sites. The primary risks of this study are: (1) breach of confidentiality leading to embarrassment or “outing” of an individual’s sexual orientation, (2) breach of confidentiality leading to disclosure of an individual’s participation in a HIV prevention intervention, (3) inconvenience and discomfort associated with interviews, and (4) potential side effects related to the uptake of PrEP

Confidentiality issues: We will collect limited personal information from participants to facilitate follow-up and will be asking personal questions about substance use, HIV risk behaviors, and sexual identity and orientation. We have outlined procedures to address maintaining confidentiality below (**see I.5**).

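### The only analysis tied to week 6 ignores Peer clustering, and the Peer-adjusted model, as its terms are listed, does not isolate the week-6 effect on which the trial is powered

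*Combined protocol and SAP*

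**What the plan says.** All sections cited are in the combined protocol and SAP.

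- **Power Analysis.** The purpose is put this way: "The primary purpose of this study is to test feasibility and to obtain an effect size estimate for a future R01 application". The calculation is for 20% (E-PrEP) vs 5% (BxNow) intending to use PrEP at 6 weeks, with 80% power, two-sided 0.05, up to 20% attrition and N = 220. It adds: "We will also have adequate power to detect a smaller effect size at 12 weeks because of our repeated measures design".
- **Analytic Plan, by visit.** At each time point, intention is compared "by using a traditional two-sample test of proportions". No Peer term is mentioned.
- **Analytic Plan, over time.** Arms are then compared with repeated-measures mixed logistic and linear models, "with the treatment arm as a fixed-effect, Peers as a random-effect, and time (as a linear term) as an independent variable". The one modification foreseen is: "We will also look at residual plots to determine if we need to include non-linear terms for time".
- **Analytic Plan, other models.** Later mixed-effects models add covariates chosen from bivariate results, and a sensitivity analysis prompted by intra-cluster correlation looks at network size and affinity to the Peer. Neither names a visit.
- **Survey times.** Under Intervention Procedures, "outcome data will be collected via online surveys at baseline, 6, and 12 weeks and after 36 weeks". In Table 2 the row "PrEP intention, use, knowledge, attitudes" is marked at weeks 0, 6, 12 and 36+. Section I.2 says: "Effectiveness measures will come from the online assessments/surveys collected at 0, 6, 12 weeks".
- **Control exposure.** The BxNow description and section I.6 give controls the E-PrEP content after week 12.

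**The concern.** The plan promises one main quantitative product, an effect size at week 6, and offers two routes to it. Neither clearly delivers it with the right precision.

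The test of proportions estimates the right quantity. However, it treats participants as independent when Peers were randomised, so its interval is too narrow whenever outcomes are correlated within Peer. The mixed model respects the randomised unit, but with a single arm term it yields one effect for all modelled visits. That equals the week-6 effect only if the effect is the same at every one of them. Baseline cannot share a real intervention effect, so whether T1 enters as a response matters, and the plan is silent on it.

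The plan itself speaks of a separate effect at week 12, yet the listed terms contain no week-12 effect either. At stake is which number, with what uncertainty, goes forward to size the next trial.

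**Working it through.** **Inputs.** From the documents: 20% vs 5% at week 6, 80% power, two-sided 0.05, 20% attrition, 240 enrolled, 16-20 Peers. Assumed, because the documents give no figure: 5% in both arms at baseline, controls constant at 5%, equal numbers at each visit, a week-12 difference of 0, 10, 15 or 20 points, and the Peer intraclass correlation (ICC).

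**1. The plan's 220.** With p1 = 0.20, p2 = 0.05, mean 0.125 and d = 0.15:
- n = [1.96·√(2·0.125·0.875) + 0.8416·√(0.20·0.80 + 0.05·0.95)]² / 0.15² = 75.1 per arm (76 rounded up).
- With continuity correction, (n/4)·[1 + √(1 + 4/(n·d))]² = 87.9, so 88 per arm.
- 2 × 88 / 0.8 = 220.

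The figure reproduces exactly, as an independent-samples comparison at week 6 with no design effect. The target is therefore a week-6 contrast of 15 points, odds ratio (0.20/0.80)/(0.05/0.95) = 4.75.

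**2. What the listed model estimates.** With balanced visits, arm is uncorrelated with time. On the risk-difference scale the arm coefficient is then the plain mean of the visit-specific differences. The odds ratios come from the matching population-averaged logistic fit.

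| Week-12 difference (points) | 0 | 10 | 15 | 20 |
|---|---|---|---|---|
| T1 a response row: (0 + 15 + d12)/3 | 5.0 | 8.3 | 10.0 | 11.7 |
| odds ratio | 2.11 | 2.94 | 3.40 | 3.89 |
| Weeks 6 and 12 only: (15 + d12)/2 | 7.5 | 12.5 | 15.0 | 17.5 |
| odds ratio | 2.76 | 4.04 | 4.75 | 5.53 |

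Adding quadratic time without an interaction leaves the arm term unchanged. A linear model of the Likert score averages in the same way, in scale units.

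**3. If an interaction was meant.**
- Arm by linear time, T1 a response row: the mean visit time is (0 + 6 + 12)/3 = 6, so the fitted week-6 difference is again the mean of the three differences (5.0, 8.3, 10.0, 11.7).
- Arm by linear and quadratic time, T1 a response row: three terms for three visits, a saturated fit that returns exactly 15.0 points at week 6 for every week-12 value.
- Arm by linear time, weeks 6 and 12 only: also saturated, so 15.0.

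**4. The unadjusted week-6 interval.** Completers: 240 × 0.8 = 192, or 12 per Peer with 16 Peers. Simulated coverage of the 95% interval for a true 20% vs 5%, with the ICC on the latent scale:

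| Latent Peer ICC | 0.02 | 0.05 | 0.10 |
|---|---|---|---|
| 16 Peers × 12 | about 93% | about 92% | about 88% |
| 20 Peers × 10 | 93.8% | 92.3% | 89.6% |

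**5. Other stated analyses.** The covariate-adjusted mixed models could in principle be fitted at week 6, but the text names no visit. The network-size and affinity analysis is not a cluster-adjusted arm contrast.

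**The case against.** **The plan may intend the right thing.** It says it compares arms over time, claims power at a specific later visit and allows non-linear time. If non-linear time were carried into an interaction with arm, the week-6 effect would be recovered exactly (step 3). That stands as a possible intention, but no interaction is written, and the non-linear provision concerns time alone.

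**T1 may not be a response.** A check for non-linear time seems to need more than two visits, which hints at T1 as a response, but T2 to T4 would also supply three. T1 intention could also enter as a covariate, because baseline differences judged relevant are to be adjusted for. With T1 out and a sustained effect there is no dilution. This stands, and it is why no single size of dilution can be claimed.

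**It is a feasibility pilot, and the week-6 proportions will be available.** True, and the point estimate from the test of proportions is on target. But an effect size is a declared primary purpose, so its interval should reflect the unit of randomisation.

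**A stronger reading is tempting:** that the effect will be understated and the next trial mis-sized. By the formula in step 1, carrying forward 10 points would give 160 per arm, and 17.5 points 71, against 88. The documents do not support this as a prediction, because they never say that the longitudinal coefficient, and not the week-6 proportions, would be carried forward.

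**Nor should the survey-count differences be read as a design fault.** Some text describes three surveys and some four, and the extracted Data Collection text shows edit marks. That is editorial. The part that matters here is that the model does not say whether T4 is included.

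**Conclusion.** The concern holds in limited form. As written, the plan gives either a week-6 estimate whose interval ignores the Peers, or a Peer-adjusted coefficient averaged over unspecified visits.

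The interval shortfall is modest at small correlations (about 93% coverage at a latent ICC of 0.02) and clearer at 0.10 (about 88%). These ICCs are assumptions.

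The gap between the averaged coefficient and the 15-point target ranges from none to 10 points over the cases in step 2. For a sustained effect it is 5 points if T1 is a response row and zero if it is not. It would also vanish under an arm-by-non-linear-time interaction, which is not stated.

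No loss of power at T1 to T3 and no size for T4 is claimed. The plan should be corrected because it leaves open which analysis yields its main estimate, and a better-defined one is available from the data already planned.

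**What to change.** - **Effect-size analysis.** Use a Peer-adjusted model of T2 and T3 intention, with arm by categorical visit and T1 intention as a covariate. Name the week-6 contrast as the effect-size estimate and week 12 as secondary.
- **Scale.** Report a marginal risk difference. The conditional odds ratio from a random-intercept logistic model is not comparable with 20% vs 5%: it would be about 5.4 to 8.1, against 4.75, at assumed latent within-person correlations of 0.2 to 0.5.
- **Small sample.** Base degrees of freedom on the number of Peers. Only 0.05 × 96 = 4.8 control events are expected at week 6, so a logistic model with Peer and participant random effects may be unstable. Pre-specify a fallback: a marginal model with Peer-level jackknife standard errors and t on (Peers − 2) degrees of freedom. In 3,000 simulated trials per case (16 Peers × 12 completers, latent Peer ICC 0.02 and 0.05), a fallback of this kind averaged 14.9 to 15.1 points at week 6 with 94.9-96.0% coverage. The two-random-effect model itself was not tested.
- **Tests of proportions.** Label them descriptive.
- **T4.** Keep it out of this model and report it separately as immediate versus delayed access, since controls will by then have been given the E-PrEP content. Reconcile the three-survey and four-survey text.

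Cost: plan wording, slightly more analysis work and a somewhat wider week-6 interval. No new data.

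### The repeated-measures models name only a Peer random effect and no within-participant covariance, so as written they give wrong standard errors for between-arm change and for participant-level factors

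*Combined protocol and SAP*

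**What the plan says.** The Analytic Plan gives the purpose and the form of the model in one sentence. The purpose is to see whether the two arms diverge during follow-up. The model class is named as "repeated measures mixed-effects logistic and linear models". The terms of that model are then listed as follows: "with the treatment arm as a fixed-effect, Peers as a random-effect, and time (as a linear term) as an independent variable". Peers are the only random effect named, and no arm-by-time term is listed.

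Under Intervention Procedures, "outcome data will be collected via online surveys at baseline, 6, and 12 weeks and after 36 weeks". Table 2 in Data Collection schedules PrEP intention at all four times; section I.2 lists only weeks 0, 6 and 12. A participant therefore contributes three or four answers.

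The Analytic Plan then applies mixed models to "selected covariates (significant in the bivariate analysis at $p < 0.1$) on the primary and secondary outcomes using mixed-effects models", and adds: "We will also assess the impact of online process and engagement variables on outcomes". Its one stated response to clustering is that "we will include a modified sensitivity analysis that examines outcomes in relation to participants' network size and perceived affinity to the Peers". The Power Analysis claims "adequate power to detect a smaller effect size at 12 weeks because of our repeated measures design".

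No residual covariance structure, generalized estimating equation or robust variance appears in the document.

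**The concern.** A Peer intercept makes all answers within one Peer's group equally correlated, whether they come from one person or from two. Stable differences between people then go partly into the residual and partly into the Peer variance. This has opposite effects on different estimates:

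- **Change over time** is a within-person comparison. Its error should contain only within-person noise, but the model charges it with between-person variation as well, so intervals are too wide.
- **Participant-level factors** vary between people. The model counts three or four answers from one person as almost that many people, so intervals are too narrow.
- **The arm main effect** is constant within Peer. Its error is set by variation between Peer means, which the Peer variance captures.

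The model's stated purpose is the first of these, and the covariate and engagement analyses depend on the second. The sensitivity analysis on network size and affinity to the Peer does not address correlation within a person.

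**Working it through.** **The plan's own figure.** For 20% against 5%, two-sided 0.05, 80% power: (1.96·√(2·0.125·0.875) + 0.8416·√(0.16 + 0.0475))² / 0.15² = 75.1, or 88 per arm after continuity correction. Then 2·88 = 176 and 176/0.8 = 220, which matches. This is a single-time comparison with no correlation term, so the point here does not change it.

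**Inputs.** 16 Peers and about 15 participants each (section I.1.2; the main text allows 16 to 20 Peers). With 20% attrition (Power Analysis), m = 15·0.8 = 12 per Peer. T = 3 visits. Assumed, because the document gives no correlations: total variance 1, Peer share sp = 0.02, and within-person correlation ρ = 0.3, 0.5 or 0.7. Hence participant variance ss = ρ − 0.02 and residual variance se = 1 − ρ.

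**Residual variance the Peer-only model would estimate** (balanced linear case):

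MSW = [(m − 1)(T·ss + se) + m(T − 1)·se] / (mT − 1)

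At ρ = 0.5: (11·1.94 + 24·0.50)/35 = 33.34/35 = 0.953.

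**Between-arm change.** The correct error variance is se, so the ratio of reported to true SE is √(MSW/se), at ρ = 0.5 √(0.953/0.50) = 1.38. If the correct test has 80% power, its expected z is 1.96 + 0.84 = 2.80. Power as written is Φ(2.80 − 1.96·1.38) = Φ(0.10), about 54%.

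**Time-constant participant covariate.** The correct variance is T·ss + se, so the ratio is √(MSW/(T·ss + se)), at ρ = 0.5 √(0.953/1.94) = 0.70. The false-positive rate is 2·[1 − Φ(1.96·0.70)], about 17%.

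| ρ | MSW | Change: SE ratio | Power instead of 80% | Covariate: SE ratio | False positives at 5% |
|---|---|---|---|---|---|
| 0.3 | 0.964 | 1.17 | 69% | 0.79 | 12% |
| 0.5 | 0.953 | 1.38 | 54% | 0.70 | 17% |
| 0.7 | 0.941 | 1.77 | 25% | 0.63 | 21% |

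With four visits at ρ = 0.5, MSW = (11·2.42 + 36·0.50)/47 = 0.949, the covariate ratio is √(0.949/2.42) = 0.63, and false positives are about 22%.

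**Time-varying covariate.** With autocorrelation a, T·ss + se becomes se + ss·(1 + 2a). At ρ = 0.5 and a = 0.5 this is 1.46, and false positives are about 11%; at a = 0.3 it is 1.27, and about 9%.

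**Simulation, linear** (16 Peers of 15, three or four visits, Peer ICC 0 to 0.05, 2,000 null runs per setting). As written, the arm-by-time SE was 1.14–1.18, 1.33–1.43 and 1.75–1.79 times the true SD at ρ = 0.3, 0.5 and 0.7, with null rejection of 0–2.5%. With a participant intercept added, the ratio was 0.98–1.02 and rejection 4.2–5.7%. The arm main-effect ratio as written was 0.96–1.02.

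**Simulation, logistic** (20% dropout; participant SD 1.8 and Peer SD 0 or 0.3 on the logit scale; 300 null runs per setting). As written: arm-by-time 1.14–1.21, rejection 1.7–2.3%; participant covariate 0.67–0.86, rejection 9–21%; arm main effect 0.87–0.96, rejection 6–9%.

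**The case against.** The plan calls these repeated-measures models and relies on that design for power, so an unstated participant structure may be intended. It nowhere says that a person's answers are treated as independent, and even the literal model makes them independent only given Peer. That stands, but the sentence lists the model's terms and stops, and on the kinder reading the covariance is still unspecified and the fix is the same.

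The change contrast needs an arm-by-time term that the plan does not list. Read literally throughout, the model tests the arm main effect, which is roughly protected. This also stands. The stated aim of comparing arms over time calls for the interaction, so it too should be written down. The later covariate and mediator models list no random effects at all; applying the Peer-only structure to them is an inference.

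The sizes come from assumed correlations. The powered endpoint is a proportion, for which the simulated change effect is smaller than the linear figure at ρ = 0.5. Table 2 re-measures several covariates, so their false-positive rates would be below those for fixed ones.

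A reader might infer that all benefit of repeated measurement is lost. It is not: with the inputs above at ρ = 0.5 and eight Peers per arm, the SE of the arm effect is √(¼·(0.02 + 0.98/12)) = 0.159 at one visit and √(¼·2.66/36) = 0.136 over three visits (2.66 = 36·0.02 + 1.94), with no participant term. A reader might also worry that an inflated Peer variance would mislead planning of the next trial. The Power Analysis speaks only of an effect-size estimate, and no section plans to use a Peer variance.

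**Conclusion.** The point holds as a specification gap with real consequences if the model is fitted as written. Between-arm change loses power: SE about 1.17 to 1.77 times too large on the linear scale for correlations of 0.3 to 0.7, and 1.14 to 1.21 in the logistic runs. Participant-level factors gain false positives: about 12% to 21% for time-constant covariates at three visits, less for time-varying ones. The directions did not change over the ranges tried; the sizes rest on the assumed correlations. The 12-week power statement is undercut for change contrasts.

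It would be tempting to conclude that the arm comparison has a badly inflated type I error or that the trial is too small. Neither follows. The arm main-effect SE is about right in the linear model. The 6–9% rejection in the logistic runs comes partly from using a normal reference with only 16 Peers, a separate matter. Severity is moderate, because feasibility and an effect-size estimate are the primary purpose and the error in the arm comparison over time is conservative.

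**What to change.** Specify random intercepts for Peer and for participant nested in Peer, or an equivalent within-participant covariance plus a Peer intercept. Apply this to every repeated-measures model, including the covariate, mediator and engagement models. State the arm-by-time term that gives the between-arm change.

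The modelling cost is one variance component and one named interaction, with no new data, provided that a person's surveys can be linked across waves. That is not settled. Section I.2 puts a study ID on each survey, collected on one platform; Data Security names another platform and says its anonymizing options will be used. Reconcile these before data collection, because without linked waves the participant effect cannot be fitted.
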